1.3.1 Investigators details

The Sponsor will maintain an updated list of Principal Investigators and investigation sites, separately from this CIP, throughout the duration of the clinical investigation. The definitive list will be provided with the Clinical Investigation Report (CIR).

Roles, responsibilities and qualifications of investigators are detailed in the CIP.

2. IDENTIFICATION AND DESCRIPTION OF THE IMD

2.1. SUMMARY DESCRIPTION OF THE IMD AND ITS INTENDED PURPOSE

The patient will be trained for the correct instillation technique of IMD. The patient will be provided with an information on the informed consent form and on the labels on the IMD boxes.

Test device: T2769 (Thealoz Total)

T2769 is a sterile, phosphate-free and pH neutral solution. It contains Trehalose, Sodium Hyaluronate (SH) and Naaga.

T2769 device is presented in the ABAK® multi-dose bottle (12.5 mL).

As per Instructions For Use (IFU), T2769 is indicated in case of moderate to severe dry eye syndrome.

Comparative device: Vismed® Multi

Vismed® Multi: eye drops presented in multi-dose container. It contains SH.

Vismed® Multi is recommended for moderate and severe dry eye conditions.

2.2. DETAILS CONCERNING THE MANUFACTURER OF THE IMD.

The legal manufacturer of T2769 according to the European (EU) Medical Device Regulation (MDR) 2017/745 is Laboratoires THÉA.

2.3. PACKAGING AND LABELLING

2.3.1 Packaging

The IMD and Hydrabak® will be packaged by approved contractor. in accordance with ISO 14155 and Regulation (UE) 2017/745. The IMDs will be prepared according to the packaging list provided by the statistician.

Hydrabak® is supplied in the ABAK® multi-dose bottle. This innovative and patented device provides eye drops through a 0.2 µm filter, preventing any bacterial contamination of the solution without the use of any preservatives.

T2769 is packaged in a multidose white polyethylene ABAK® system bottle. The dispenser is already used in several currently marketed eye drops. This innovative and patented device provides eye drops through a 0.2 µm filter, preventing any bacterial contamination of the solution without the use of any preservatives:

[figure not shown]

Figure 1. Diagram of the ABAK® III bottle

The complete treatment for one patient and for the complete investigation duration will be as following:

Each patient will receive 1 preservative-free multidose bottle of Hydrabak® (ABAK system) during the run-in period and 4 preservative-free multidose bottles of the IMD during the investigation.

2.3.2 Labelling

All labels will be written in the local language. The content of the labelling is in accordance with ISO 14155 and Regulation (UE) 2017/745 specifications and requirements.

Each bottle of run-in treatment and IMD will carry one label.

The cardboard box of Hydrabak will also carry a detachable label (flag label) bearing at least the CIP number and the batch number.

The cardboard carton of IMD will also carry a detachable label (flag label) bearing at least the CIP number and IMD number. This label will be torn off by the person dispensing the IMD to the patient and will be stuck in the space provided in the IMD allocation form in order to record the dispensing procedure.

2.4. INTENDED PURPOSE OF THE IMD IN THE PROPOSED CLINICAL INVESTIGATION

T2769 is intended to hydrate and soothe itchy, red or irritated eyes in case of moderate to severe dry eye syndrome (patients over or equal than 18 years excluding pregnant or breastfeeding women).

2.5. THE POPULATIONS AND INDICATIONS FOR WHICH THE IMD IS INTENDED

T2769 is suitable for adults.

2.6.DESCRIPTION OF THE IMD

T2769 is an ophthalmic solution composed of trehalose (3%), sodium hyaluronate (0.15%), N-acetyl aspartyl glutamic acid sodium salt (NAAGA, Na 2.45%), NaOH 0.1N, Water for injections and Nitrogen.

T2769 is a sterile, phosphate-free and pH neutral solution.

The solution is supplied in the ABAK® multi-dose bottle. This innovative and patented device provides eye drops through a 0.2 µm filter, preventing any bacterial contamination of the solution without the use of any preservatives

T2769 should be used within 3 months after first opening of the ABAK® container.

Table 3 Investigational Medical Device T2769

Names of ingredients	Percentage formula (g/100 ml)	Function	Reference to standards
Trehalose dihydrate*	3.00*	Lubricating, hydrating agent	Current Eur. Ph. [2297]
N-acetyl aspartyl glutamic acid, sodium salt (NAAGA, Na)*	2.45*	Soothing agent	[REDACTED]
Sodium hyaluronate**	0.15*	Lubricating, hydrating agent	Current Eur. Ph. [1472]
NaOH 0.1N***	qsp pH 7.2	pH adjustment	Current Eur. Ph. [0677]
Water for injections	qsp 100 ml	Vehicle	Current Eur. Ph. [0169]
Nitrogen	-	Ad preparation and storage	Current Eur. Ph. [1247]

* The quantity of the ingredient (Trehalose dihydrate and Naaga Na) is adjusted as a function of its titre and water content

** The quantity of this ingredient is adjusted as a function of its water content

*** A diluted solution of NaOH is used to adjust pH around 7.2

The excipients of the T2769 eye-drops (NaOH, water for injections and Nitrogen) are well-known and commonly used in ophthalmic formulations.

Batch number and expiry dates will be provided in the certificate of analysis and will be specified on the packaging.

2.7. STORAGE CONDITIONS AND INSTRUCTIONS OF USE

All IMD should be stored in its original packaging, protected from light and moisture, at a temperature between 8 and 25°C and the expiry date refers to the last day of that month as long as the packaging is intact, and it has been stored correctly.

Do not refrigerate or freeze.

Until dispensed to the patient, products should be in a secure area with restricted access. The investigator, the hospital pharmacist or other personnel allowed to store and dispense IMD(s) will be responsible for ensuring that the IMD(s) are securely maintained as specified by the Sponsor and in accordance with the applicable regulatory requirements.

T2769 should not be used after the expiry date indicated on the outer cardboard box.

The product can be used until 24 months before opening and 3 months after first opening. The expiry date refers to the intact correctly stored packaging.

The IMD should not be used if the bottle is damaged.

If significant changes and/or update on labelling, handling and storage are required during the investigation, the corresponding sections will be updated by notifying or submitting to Competent Authorities (CAs) concerned accordingly. All investigators' sites will be immediately informed about any change by the Sponsor, investigator or a delegate will inform the patient, if any.

Accordingly, the Sponsor may decide to halt temporary the recruitment (see **Section 16.1**). In any way, the reasons and the procedures for any changes will be justified and described by the Sponsor.

2.8. INVESTIGATOR BROCHURE AND INSTRUCTIONS FOR USE

All details concerning the IMD are specified in separate documents as the *IB and the IFU*. These documents will be updated whenever necessary and all applicable versions will be provided to each investigation site throughout the clinical investigation.

At time of writing the CIP, validated and applicable versions are

- For the IB: V3, MAR-2023
- For the IFU: V8, MAR-2023

2.9. DESCRIPTION OF COMPARATIVE DEVICE

Vismed® Multi is purchased from Horus Pharma.

Vismed® Multi is a sterile solution for ocular use.

Packaging and labelling are provided in Section 2.32.3.

Batch number and expiration dates will be specified on the packaging.

[figure not shown]
Storage conditions are specified in **Section 2.7**.

[figure not shown]
[figure not shown]
Table 4 Vismed® Multi details the composition and function of the comparative device Vismed® Multi.

[figure not shown]
[figure not shown]
Table 4 **Vismed® Multi**

[figure not shown]
Name of ingredients	Formula Per 100 mL
HA, sodium salt	0.18%
Sodium chloride	0.279%
Potassium chloride	0.103 g
Magnesium chloride	0.0092%
Calcium chloride	0.0089%
Disodique hydrogenophosphate,	0.032%
Sodium citrate	0.0026%
Hydrochloric acid	Ad pH 7.2 – 7.4
Purified water, to	100 mL

3. JUSTIFICATION FOR THE DESIGN OF THE CLINICAL INVESTIGATION

3.4 DESCRIPTION OF THE CLINICAL DEVELOPMENT STAGE

The investigation is defined as a pre-market, pivotal stage (cf ISO 14155:2020). The clinical investigation design is confirmatory.

[figure not shown]
4. BENEFITS AND RISKS OF THE IMD, CLINICAL PROCEDURE AND CLINICAL INVESTIGATION

4.1 ANTICIPATED CLINICAL BENEFITS

The following clinical benefits are expected with the use of T2769:

- Improvement of (global) ocular comfort and relief from the symptoms of dry eyes
- Soothing of ocular sensations (from itchiness and irritations)
- Reduction of the redness of the eyes
- Good level of tolerance on the eye

4.3 RISKS ASSOCIATED WITH PARTICIPATION IN THE CLINICAL INVESTIGATION

Laboratoires Théa performed a risk analysis according to the current ISO 14971 standard.

All risks identified in Laboratoires Théa's risk analysis were mitigated. The remaining residual risks were considered to be of negligible or acceptable levels. The risks mitigated to this latter risk level (acceptable) are the following:

[figure not shown]
[figure not shown]
- The device is not biocompatible (use of the device beyond the expiry date)
- The product is not sterile (loss of the sterile barrier due to inappropriate storage conditions by the user)
- The device is contaminated (the user lets the tip of the container touch something (eye, eyelid, objects, user's hand OR the user shares the device with another person (cross contamination))
- The device leaks (primary packaging deterioration due to inappropriate storage conditions)
- The patient gets hurt while using the device (the user uses a sharp object to remove the cap/open the device and damages the device and/or gets hurt OR the patient drives or uses machines while experiencing blurred vision)
- Continuous use of the device is not ensured (the user uses another product by mistake)
- A child swallows a component of the device (bottle cap)

All the possible warnings have been put in place in the instructions for use as well as on the secondary and primary packaging if possible.

These hazards cannot arise in the normal conditions of use.

4.4 POSSIBLE INTERACTIONS WITH CONCOMITANT MEDICAL TREATMENTS

To avoid possible interactions with a concomitant treatment, patients should be asked to wait at least 15 minutes between using two different eye products.

5. OBJECTIVES AND HYPOTHESES OF THE CLINICAL INVESTIGATION

5.1 CLAIMS FOR CLINICAL PERFORMANCE, EFFECTIVENESS OR SAFETY OF THE IMD

There is no claim concerning the clinical performance of THEALOZ TOTAL in the IFU. However, the following clinical performances support the claimed clinical benefits:

- THEALOZ TOTAL reduces ocular surface damages
- THEALOZ TOTAL increases tear film stability/quantity

As per the IFU, the claim on clinical safety of THEALOZ TOTAL is:

- THEALOZ TOTAL is well tolerated on the ocular surface

As per the IFU, the clinical benefits of THEALOZ TOTAL are:

[figure not shown]
- THEALOZ TOTAL relieves from the symptoms of dry eyes
- THEALOZ TOTAL soothes the eyes (from itchiness and irritation sensations)
- THEALOZ TOTAL reduces the redness of the eyes

As per Laboratoires THEA, other clinical benefit of THEALOZ TOTAL is:

- THEALOZ TOTAL improvement of (global) ocular comfort

5.2 OBJECTIVES, PRIMARY

[figure not shown]
The primary objective of the investigation is to demonstrate the non-inferiority of T2769 *versus* Vismed® Multi in terms of total ocular surface staining (Oxford score) in patients with DES, after 35 days of treatment.

5.3 SCIENTIFIC JUSTIFICATION AND CLINICAL RELEVANCE FOR EFFECT SIZES, NON-INFERIORITY MARGINS OR EQUIVALENCE LIMITS

Estimation of the standard deviation and determination of the non-inferiority limit are based upon data of previous studies and literature.

Concerning the non-inferiority limit, according to clinicians, a variation of 2 points in the total Oxford grade, which corresponds to a variation of less than 1 grade in the three areas (corneal, temporal and nasal), is considered as not clinically significant.

6. DESIGN OF THE CLINICAL INVESTIGATION

6.1 GENERAL

6.1.1 Justification of the Investigation Design

Methodology: A 5-week, international, multicentre, randomised, investigator-masked, 2 parallel groups (T2769 versus Vismed® Multi) investigation in DES patients.

- Multicentre investigation

The investigation will be performed in different sites in EU and outside EU.

Multicentre (and multi-investigator) design will provide the possibility of recruiting the patients from a wider population and of using the device in a broader range of clinical settings, thus presenting an experimental situation that is more typical of future use. In this case, the involvement of a number of investigators also gives the potential for a wider range of clinical judgment concerning the value of the therapeutic intervention. In addition, it is also a practical mean of accruing sufficient patients to satisfy the investigation objective within a reasonable timeframe.

- Randomised

At the randomisation visit on Day 1, patient fulfilling all eligible criteria will be randomly assigned to 1 of the 2 treatment groups. Randomisation allows keeping the investigator's masking about the product use for DES treatment. It is generally considered the most reliable method for evaluating the effects of interventions.

- Choice of run-in period

Patients meeting the screening criteria will undergo a 7-10-day run-in period. During this period, all patients will substitute their current treatment with Hydrabak®, ophthalmic solution containing NaCl 0.9%.

[figure not shown]

- Investigator-masked

A double-masked investigation design is not possible due to different commercial packaging between T2769 – Vismed® Multi.

However, the identity of the IMD given to each patient will not be known for the masked investigator who is independently in charge of the ophthalmic examination.

To this aim, the masked investigator will differ from the person who will record the used/unused IMDs. The recording will be delegated either to the hospital pharmacy or to a trained collaborator (trained by the masked investigator; hereafter referred to as unmasked collaborator). Therefore, the masked investigator should not receive the returned IMDs from the patients.

- Scheme of administration

The dose regimen recommended is 3 to 6 times daily.

- Choice of primary endpoint

The primary [REDACTED] endpoints of this clinical study (total ocular surface staining (Oxford scale), [REDACTED]

[REDACTED] have been taken into consideration based on the clinical literature review (Jones et al. 2017; Aragona et al. 2019; Fariselli et al. 2018; Mateo Orobio et al. 2017; Nasser et al. 2018; Pinto-Bonilla et al. 2015; Chiambaretta et al. 2017). Consequently, these endpoints are clinically relevant, clearly defined and assessed at specified time points in order to provide clinical evidence on the efficacy [REDACTED] of T2769 in its intended use (i.e., improvement of the ocular signs and symptoms in DED patients).

- Symptom assessment

Ocular symptoms (except upon instillation, not assessed at inclusion) as well as AEs will be assessed at all investigation visits.

The investigation flow chart is described in **Table 2**.

6.1.2 Description of the Measures to be Taken to Minimize or Avoid Bias

6.1.2.1 Randomisation

A randomised design has been chosen to ensure a balanced allocation to the assignment of device arms of all patient's known and unknown characteristics. Randomisation helps to avoid possible bias in the selection and allocation of patients arising from the predictability of device assignments.

The randomisation code list stratified by site and lists of IMDs numbers for the packaging is generated by the Interactive Web Response System (IWRS) provider. Patients will be randomised on a 1:1 basis to T2769 or Vismed® Multi respectively.

Randomisation list(s) and lists of IMDs numbers for the packaging are to be kept in security by the editor (IWRS provider) according to their procedures.

The packaging list is to be kept by the company responsible for manufacturing and labelling of the treatment unit.

The randomisation and the IMD kit number will be allocated to the patients according to randomisation list using an Interactive Response Technology (IRT).

Randomisation will occur at Randomisation visit (Day 1; Visit#2) after all procedures have been performed and eligibility for the investigation confirmed. The patient who meets the eligibility criteria will be randomly assigned to treatment and associated to a randomisation number.

6.1.2.2 Masking and Code Breaking

Serious biases may occur in a clinical investigation including investigator bias (which may arise due to knowledge by the investigator of treatment allocated to a particular patient), evaluator bias and placebo effects. To protect an investigation against these potential biases, masking will be used.

This will be an investigator-masked clinical investigation.

The **masked investigator** will remain masked to the IMD (T2769 – Vismed® Multi). He/She will not receive the returned IMD from the patients.

The following-up and the number of returned IMDs will be recorded by **unmasked collaborator** throughout the clinical investigation.

The unmasked collaborator will also be in charge of returned/unreturned IMD (T2769 – Vismed® Multi) counting.

Masking will be achieved by coding the interventions, providing each product unit with identical cardboard box and by identifying it by an IMD kit number.

The code should not be broken except:

- in case of medical emergency (where knowledge of the IMD received would affect the treatment of the emergency),
- or when it is a regulatory requirement (e.g., for Unanticipated Serious Adverse Device Effect [USADE]).

The investigator is responsible for accessing the IRT System to obtain the name of the IMD received by the patient.

If an emergency code breaking becomes necessary, the investigator should notify the Sponsor.

When a code is broken, the date, time and reason must be recorded in the patient's Source, and in any associated AE report. The identity of the IMD should not be disclosed in these documents.

Further to a USADE assessment by the Global Drug Safety & Medical Information Department, the code might be broken for reporting purposes. The relevant Laboratoires THÉA, Contract Research Organization (CRO) and masked investigator and masked staff remain unaware of the identification of the IMD as per the above-mentioned process.

The overall randomisation list will be broken for data analysis after database lock.

6.1.2.3 Dispensing

IMD will be dispensed by the masked collaborator and/or pharmacist delegate for selected tasks. Each IMD dispensation will be recorded in the related documentation.

During the whole investigation treatment period, the **masked investigator and/or delegate** will remain masked to the IMD (T2769 – Vismed® Multi). He/she will not receive the returned IMD from the patients.

All information regarding the usage of the IMDs will be contained in the package given to patients.

The IMDs must be dispensed only to patients in accordance with the Clinical Investigational Plan (CIP) and the randomisation.

Once all screening criteria have been checked, the patient will receive a box including Run-in Hydrabak® treatment for the run-in period.

At the randomisation visit#2 (Day 1), once inclusion and exclusion criteria have been checked and once the patient is eligible, the randomisation will be performed and the IRT will provide the IMD kit number allocated to the patient.

At the other visit (visit#3, Day 15 days \pm 1 day after the randomisation) with dispensation, the IRT will provide the IMD kit number allocated to the patient.

Two dispensations will be performed as follows:

- At randomisation visit#2(Day 1): one box containing enough bottles for the treatment period Day 1 to Day 15 \pm 1 day will be provided by the investigator (or delegate) or pharmacist with the number assigned by the IRT.
- At Visit#3 (Day 15): one box containing enough bottles for the treatment period Day 15 \pm 1 day to Day 36 + 3 days will be provided by the investigator (or delegate) or pharmacist with the number assigned by the IRT.

The site team member will instruct patient on the method of instilling the doses and will train his / her patient to not disclose the IMD characteristics neither during the visit not when reporting / discussing AE / Device Deficiency (DD).

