Visit#2 will consist of the following procedures and examinations to be done according to the following order and in each eye.

Visit#2 will consist of the following procedures and examinations by the masked investigator or authorised delegate who will perform the ophthalmologic examination during all the visits.

By the masked investigator (the same as the screening visit) **or delegate for selected tasks** (according to local requirements, the investigator may delegate tasks to collaborator)

- ✓ On paper CRF
- Questionnaire (OSDI)
- Ocular discomfort (VAS)

- ✓ On eCRF
- Questioning about ocular symptoms within the last 48 hours
- Questioning about Hydrabak® compliance during run-in period and last instillation (at least 6 hours) before the visit and check of the patient diary completion with the patient,
- Questioning about previous and concomitant ocular and non-ocular treatments
- Slit lamp examination for measuring*:
 - Measurement of conjunctival hyperaemia with [REDACTED] photographic scale
 - TBUT
 - Oxford 0-15 grading scheme (corneal and conjunctival staining by fluorescein, with a yellow filter),
- Schirmer test* (without anaesthesia),
- AE reporting
- Verification of inclusion and exclusion criteria
- Status of the patient
- Randomisation
- IMD dispensation

- Patient diary dispensation. The patient who will be instructed to instil the IMD in both eyes and report in the patient diary the number of instillations/day and to bring back it at each visit.

* Examination must be performed by the same **masked investigator or delegate for selected tasks** for all visits and using the same slit lamp.

The next visit must be scheduled in 15 days (± 1 day) at the same hour (± 4 hours).

Visit#3: Day 15 (± 1 day)

Visit#3 will consist of the following procedures and examinations to be done according to the following order and in each eye.

By the masked investigator (the same as the screening visit) **or delegate for selected tasks** according to local requirements, the investigator may delegate tasks to collaborator)

- ✓ On paper CRF
- Questionnaire (OSDI)
- Ocular discomfort (VAS)

- ✓ On eCRF
- Questioning about ocular symptoms upon instillation
- Questioning about ocular symptoms within the last 48 hours
- Questioning about soothing sensation 15 min after IMD instillation
- Assessment of global patient satisfaction with the use of bottle
- Assessment of global satisfaction by the patient
- Assessment of the ocular tolerance by the patient

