- Questioning about ocular and non-ocular concomitant treatments
- Review of the completion patient diary
- Questioning about IMD dose regimen compliance
- Slit lamp examination for measuring*:
 - Measurement of conjunctival hyperaemia with [REDACTED] photographic scale
 - TBUT
 - Oxford 0-15 grading scheme (corneal and conjunctival staining by fluorescein with a yellow filter),
- Schirmer test* (without anaesthesia),
- AE reporting
- Device deficiency
- Assessment of the ocular tolerance by the investigator
- Assessment of the performance by the investigator

* Examination must be performed by the same **masked investigator or delegate for selected tasks** for all visits and using the same slit lamp.

By the unmasked collaborator:

- Recording the number of returned used and unused IMD in document source (the accountability is expected for the amount of bottles) and transfer this information to masked investigator.

The next visit must be scheduled at Day 36 later (+3days)

Visit#4: Day 36 (+3days)

Visit#4 will consist of the following procedures and examinations to be done according to the following order and in each eye.

By the masked investigator (the same as the screening visit) or delegate for selected tasks (according to local requirements, the investigator may delegate tasks to collaborator).

- ✓ On paper CRF
- Questionnaire (OSDI)
- Ocular discomfort (VAS)

- ✓ On eCRF
- Questioning about ocular symptoms upon instillation questionnaire
- Questioning about ocular symptoms within the last 48 hours
- Questioning about soothing sensation 15 min after IMD instillation
- Assessment of global patient satisfaction with the use of bottle
- Assessment of global satisfaction by the patient
- Assessment of the ocular tolerance by the patient
- Questioning about ocular and non-ocular concomitant treatments
- Measurement of Far Best Corrected Visual Acuity,
- Review of the completion patient diary
- Questioning about IMD dose regimen compliance
- Slit lamp examination for measuring*:
 - Measurement of conjunctival hyperaemia with [REDACTED] photographic scale
 - TBUT
 - Oxford 0-15 grading scheme (corneal and conjunctival staining by fluorescein, with a yellow filter),
- Schirmer test* (without anaesthesia),
- AE reporting
- Device deficiency
- Assessment of the ocular tolerance by the investigator
- Assessment of the performance by the investigator
- Status of the patient

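### Masked staff, including the examining investigator, may dispense products that differ inside identical cartons, and no rule separates dispensing or instillation training from Oxford grading

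*Protocol*

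**What the plan says.** **Dispensing.** Protocol 6.1.2.3 opens with "IMD will be dispensed by the masked collaborator and/or pharmacist delegate for selected tasks". For the Day 1 and Day 15 dispensations it then says that the box "will be provided by the investigator (or delegate) or pharmacist with the number assigned by the IRT". In 6.1.4, the Visit 2 task list is headed "By the masked investigator (the same as the screening visit" and extends to a delegate. It includes "IMD dispensation" and gives no task to an unmasked person.

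**Training.** The same section says "The site team member will instruct patient on the method of instilling the doses". The masking status of that person is not given. The sentence goes on to require that patients be taught not to reveal the product's characteristics.

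**What is masked.** Protocol 6.1.2.2 relies on coding and on "providing each product unit with identical cardboard box and by identifying it by an IMD kit number". Protocol 6.1.1 explains the investigator-masked design: "A double-masked investigation design is not possible due to different commercial packaging".

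**Separation of roles.** Protocol 6.1.1, 6.1.2.2, 6.1.4 and 11.1.1, and SAP 2.2.2, keep the masked investigator away from returned product. An unmasked collaborator (11.1.1 adds a pharmacist) receives, counts and records it. Sections 6.1.1 and 6.1.2.3 state the aim that the examiner should not know the product.

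**The concern.** Patients know which bottle they hold, so masking the examiner is the main protection against biased assessment. The primary endpoint is the change in Oxford staining grade at D36, a clinician's score read at the slit lamp by the same person at every visit. Protocol 6.1.2.2 itself lists investigator and evaluator bias as serious threats.

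By keeping returned bottles from the grader, the protocol accepts that sight of the bottle can unmask. The outgoing bottles are the same products, yet masked staff may hand them out, and nothing stops the grader from being the person who teaches instillation.

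A grader who learned the product on Day 1 would carry that knowledge into the D15 and D36 gradings, both of which enter the primary mixed model. Success requires the upper 95% confidence bound for T2769 minus Vismed Multi to lie below 2 points. Grading that leaned towards T2769, or that narrowed a true disadvantage, would make that easier to meet; leaning the other way would make it harder. The documents do not indicate a direction.

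**Working it through.** The point concerns procedure, so the check sets the assignments side by side.

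| Step | Assigned to | Masking status | Protocol section |
|---|---|---|---|
| Dispensing, general rule | masked collaborator, or pharmacist delegate | masked, or pharmacist | 6.1.2.3 |
| Dispensing, Day 1 and Day 15 | investigator, delegate or pharmacist | not stated here | 6.1.2.3 |
| Dispensing, Visit 2 list | masked investigator or delegate | masked | 6.1.4 |
| Dispensing, Visit 3 list | no item | none given | 6.1.4 |
| Instillation training | site team member | not stated | 6.1.2.3 |
| Returns and counting | unmasked collaborator (or pharmacist) | unmasked | 6.1.1, 6.1.2.2, 6.1.4, 11.1.1 |
| Oxford grading | same masked person at all visits | masked | 6.1.4 |

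1. *Could this be a one-word slip?* The term masked collaborator occurs only in 6.1.2.3, while the other sections speak of an unmasked collaborator, so a drafting error is plausible. Correcting that word would still leave the investigator or delegate as dispenser at both dispensations, and the Visit 2 list as it stands. The word investigator is unqualified in the dispensation rules, but the text describes no unmasked investigator.

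2. *Does handling the carton reveal the product?* Not in itself. The carton is identical and coded. Section 2.3.2 has the dispenser tear off a flag label carrying at least the plan number and the IMD number, and does not mention opening the carton. The product would be exposed if the carton were opened or the bottle shown.

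3. *Is that step excluded?* No. Training is required (2.1 and 6.1.2.3). The text does not say whether the real bottle is used, whether the carton stays closed on site, or that the trainer must be someone other than the grader.

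4. *Which gradings are exposed?* Randomisation follows all Visit 2 procedures (6.1.2.1), and dispensing comes after the slit-lamp examination in a list to be followed in order (6.1.4). The baseline grade is therefore protected. The D15 grade follows one dispensing and the D36 grade follows two.

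5. *Can the size be calculated?* No. It would need the share of patients whose grader dispensed or trained, how often the bottle was then seen, and the resulting shift in grade. The documents give none of these, nor, in the public text, the SD of the endpoint. An error rate built on assumed values would only restate the assumptions.

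**The case against.** A reader might infer that the grader sees the product. The documents do not support that. A closed, coded carton is compatible with masking, and opening it is never described. Section 6.1.1 states that the examiner will not know the product, and 6.1.2.3 repeats that the masked investigator or delegate stays masked. Patients are trained not to disclose. A pharmacist may dispense, and a delegate who dispenses need not be the grader. Section 6.4 leaves detailed procedures to an investigator manual, and the visit schedule (Table 2) is not in the available text; either might define the roles.

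Most of this stands, and it limits the point to a missing safeguard. It does not remove it: a stated aim is not a procedure, non-disclosure training governs what patients say and not what staff see, and the pharmacist is optional.

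Two further inferences should be resisted:

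- *That masked staff are required to teach instillation.* The trainer is simply undefined and could be masked or unmasked.
- *That the bottle counts unmask.* The unmasked collaborator must "transfer this information to masked investigator", but what is passed on is the number of used and unused bottles. Both arms receive 4 bottles (6.2.4), so a count does not identify the arm. No change is needed there.

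**Conclusion.** The point holds as a gap in role assignment. Protocol 6.1.2.3 and the Visit 2 list in 6.1.4 permit masked staff, including the examining investigator, to dispense products distinguishable inside the carton. The trainer's masking status is undefined, and the only stated separation from grading concerns returned product. The result is an avoidable, unguarded route to unmasking the grader of the primary endpoint.

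It is not evidence that unmasking occurs, and no size or direction of bias can be given. The conclusion rests on the available text; it would weaken if the investigator manual or Table 2 already gives dispensing and training to someone who does not grade. The change is worth making because it is cheap and protects the primary endpoint.

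**What to change.** Reconcile Protocol 6.1.1, 6.1.2.2, 6.1.2.3 and the visit lists in 6.1.4:

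- State that dispensing at Visits 2 and 3 and instillation training are done only by the unmasked collaborator or a pharmacist, and that this person never grades staining.
- State that both take place after that visit's examinations, with the carton kept closed to the masked investigator.
- In 6.1.2.3, delete the masked collaborator and the investigator or delegate as dispensers.
- In 6.1.4, move the Visit 2 dispensing item to the unmasked collaborator or pharmacist, and add it under that role at Visit 3, where the list has no dispensing item although 6.1.2.3 plans one.

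The cost is protocol wording and updated delegation logs. The unmasked collaborator role already exists. The one practical burden is that this person or a pharmacist must be available when product is handed out at Visits 2 and 3.

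If patients have already been treated under the present text, the dispensing records (6.1.2.3) and the assessor identification in the source documents (6.5.1) could be compared, as far as they name the dispenser, to report how often dispenser and grader were the same person.
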